4. GENERAL STATISTICAL CONSIDERATIONS

In general and unless otherwise noted, continuous variables will be summarised using the following summary statistics; N, Mean, Standard Deviation, Median, Minimum and Maximum. Categorical variables will be summarized using frequency tabulations (i.e., counts and percentages). In the case of missing categorical data, an “unknown” category will be created for reporting purposes, but subjects or records included in this category will not be included in the denominator when calculating percentages.

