8.7. Dose Modifications

Dose reductions and interruptions will be summarized for subjects who had at least one dose reduction or interruption. In addition, summary statistics (frequency of patients and median number of days) will be produced for time to first dose reduction/interruption as well as the number of reduction/interruptions per subject.

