10.1.3. Time to Event Analyses

Four time to event endpoints (DoR, TTP, PFS, and OS) will be analysed for this study. Response values (as determined by the site investigator based on the IMWG uniform response criteria) categorised as PD, relapse and relapse after CR indicate that the subject had a disease progression, while other response values (i.e. sCR, CR, VGPR, PR and SD) indicate that the subject did not have a disease progression.

For each time to event endpoint, the Kaplan-Meier method will be used to estimate the survival distribution function. The median, 25 and 75 percentile of the survival distribution along with

the two-sided 95% CI for the median will be estimated. In addition, the event rates at 6, 12 and 24 month time-points will be computed, along with the standard errors. The plots of survival curves using Kaplan-Meier estimates will be presented as appropriate.

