- muscular weakness
- glucose intolerance
- mood alteration
- cataract
- cardiovascular events/dysrhythmia
- fluid retention/edema
- hematopoietic cytopenias

In addition the following tables will be presented to further investigate the corresponding AEs of interest:

- treatment emergent neutropenia and febrile neutropenia by GCSF usage on study
- treatment emergent arterial thrombotic events with and without prophylaxis medications (where prophylaxis medication is defined as low-dose aspirin, low molecular weight heparin, or other equivalent antithrombotic or anticoagulant within one week of prior to onset of event)
- treatment emergent venous thrombotic events with and without prophylaxis medications (where prophylaxis medication is defined as low-dose aspirin, low molecular weight heparin, or other equivalent antithrombotic or anticoagulant within one week of prior to onset of event)
- treatment emergent DVT with and without concurrent PE (where concurrent PE is defined as PE onset within +/- two weeks of onset of DVT, and before resolution of DVT)
- treatment emergent neuropathy by baseline neuropathy status
- time to onset of neuropathy from enrollment
- time to improvement/resolution of neuropathy from enrollment
- time to worsening/new incidence of neuropathy from enrollment
- neuropathy still ongoing at treatment discontinuation
- treatment emergent grade 3 or higher infections and infestations and concurrent neutropenia (where concurrent grade 3 or 4 neutropenia is defined as grade 3 or 4 neutropenia onset within +/- two weeks of onset of infection and infestation, and before resolution of infection and infestation)
- treatment emergent grade 3 or higher neutropenia and concurrent infections and infestations (where concurrent grade 3 or 4 infections and infestations is defined as grade 3 or 4 infections and infestations onset within +/- two weeks of onset of neutropenia, and before resolution of neutropenia)
- treatment emergent (grade 3 or higher) thrombocytopenia with concurrent haemorrhage and bleeding (where concurrent bleeding is defined as bleeding onset within +/- two weeks of onset of thrombocytopenia, and before resolution of thrombocytopenia)

- treatment emergent (grade 3 or higher) haemorrhage and bleeding with concurrent thrombocytopenia (where concurrent grade 4 thrombocytopenia is defined as grade 4 thrombocytopenia onset within +/- two weeks of onset of bleeding, and before resolution of bleeding)

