14.3.2.16.6	Treatment Emergent Serious Adverse Events of Interest: Safety Population
14.3.2.16.7.1	Treatment Emergent Serious Adverse Events of Interest Related to Any Study Drug: Safety Population
14.3.2.16.7.2	Treatment Emergent Serious Adverse Events of Interest Related to Pomalidomide: Safety Population
14.3.2.16.7.3	Treatment Emergent Serious Adverse Events of Interest Related to Low-Dose Dexamethasone: Safety Population
14.3.2.16.7.4	Treatment Emergent Serious Adverse Events of Interest Leading to Discontinuation of Any Study Drug: Safety Population
14.3.2.16.7.5	Treatment Emergent Serious Adverse Events of Interest Leading to Discontinuation of Pomalidomide: Safety Population
14.3.2.16.7.6	Treatment Emergent Serious Adverse Events of Interest Leading to Discontinuation of Low-Dose Dexamethasone: Safety Population
14.3.2.16.8.1	Treatment Emergent Adverse Events of Interest Leading to Discontinuation of Any Study Drug: Safety Population
14.3.2.16.8.2	Treatment Emergent Adverse Events of Interest Leading to Discontinuation of Pomalidomide: Safety Population
14.3.2.16.8.3	Treatment Emergent Adverse Events of Interest Leading to Discontinuation of Low-Dose Dexamethasone: Safety Population
14.3.2.16.9	Treatment Emergent Adverse Events of Interest by CTCAE Grade 1/2 and 3/4: Safety Population
14.3.2.16.10	Treatment Emergent Adverse Events of Interest by CTCAE Grade: Safety Population
14.3.2.16.11	Treatment Emergent Neutropenia by GCSF Usage on Study: Safety Population
14.3.2.16.12.1	Treatment Emergent Arterial Thrombotic Events With and Without Prophylaxis Medications: Safety Population

14.3.2.16.12.2	Treatment Emergent Venous Thrombotic Events With and Without Prophylaxis Medications: Safety Population
14.3.2.16.12.3	Treatment Emergent DVT With and Without Concurrent Pulmonary Embolism [a]: Safety Population
14.3.2.16.13.1	Treatment Emergent Neuropathy by Baseline Neuropathy Status: Safety Population
14.3.2.16.13.2	Time to Onset of Neuropathy: Safety Population
14.3.2.16.13.3	Time to Improvement/Resolution of Neuropathy from Baseline: Safety Population (Subjects with Improvement/Resolution of Baseline Neuropathy)
14.3.2.16.13.4	Time to Worsening/New Incidents of Neuropathy from Baseline: Safety Population (Subjects with Worsening Baseline of Neuropathy or New Incidents of Neuropathy)
14.3.2.16.13.5	Neuropathy Still Ongoing at Treatment Discontinuation: Safety Population (Subjects Who had Treatment Emergent Neuropathy with Neuropathy Ongoing at Baseline)

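### The tables for time to neuropathy improvement and time to neuropathy worsening include only subjects who had the event, with no censored analysis, so the tabulated times are biased short

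*SAP*

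**What the plan says.** SAP Section 11.1.1, under adverse events of special interest, plans "time to improvement/resolution of neuropathy from enrollment" and "time to worsening/new incidence of neuropathy from enrollment". It gives no at-risk set, censoring rule or estimator for either.

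The populations appear only in the Appendix B table titles:

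- Table 14.3.2.16.13.3: "Time to Improvement/Resolution of Neuropathy from Baseline: Safety Population (Subjects with Improvement/Resolution of Baseline Neuropathy".
- Table 14.3.2.16.13.4: "Time to Worsening/New Incidents of Neuropathy from Baseline: Safety Population (Subjects with Worsening Baseline of Neuropathy or New Incidents of Neuropathy".
- Table 14.3.2.16.13.2, the neighbouring table, has no such restriction: "Time to Onset of Neuropathy: Safety Population".

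Two general provisions settle how the times would be summarised. Section 4 sets the default: "continuous variables will be summarised using the following summary statistics; N, Mean, Standard Deviation, Median, Minimum and Maximum". Section 10.1.3 reserves Kaplan-Meier estimation for efficacy: "Four time to event endpoints (DoR, TTP, PFS, and OS) will be analysed for this study". Neuropathy times are not among the four.

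**The concern.** A subject with neuropathy at baseline that never improves does not enter the improvement table. Nor does a subject who might have improved later but whose observation ended first. The worsening table has the same gap. What remains is the set of events that came early enough to be seen, and among these short times are over-represented.

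Early end of observation is to be expected here. Under Section 3.1, treatment stops for progression, toxicity, death, withdrawal and other reasons, and the first full analysis takes place once all subjects have completed up to 2 cycles unless they stopped earlier. The study's primary objective is safety. A reader who takes the tabulated median as the time a typical subject with neuropathy needs to improve, or takes to worsen, would get too short a time in both tables.

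**Working it through.** The SAP states no figure for these times, so there is none to reproduce. The check concerns the direction and possible size of the bias.

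**Direction.** Let T be the event time and C the time at which observation ends, independent of T. Among subjects whose event is seen (T ≤ C), the density of T is proportional to f(t) × P(C ≥ t). The weight P(C ≥ t) never increases with t, so the distribution can only move towards shorter times. This needs independence of T and C but no particular distribution.

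**Size, under assumed exponential times.** Let M be the true median time to event and C now the median observation time, both in months and both assumptions. Event times among subjects with the event are then exponential with the sum of the two rates, which gives:

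- event-only median = 1/(1/M + 1/C) = M·C/(M + C)
- share with the event seen = C/(M + C)

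| True median M | Median observation C | Share seen | Event-only median |
|---|---|---|---|
| 6 | 5 | 5/11 = 45% | 30/11 = 2.73 |
| 12 | 5 | 5/17 = 29% | 60/17 = 3.53 |
| 24 | 5 | 5/29 = 17% | 120/29 = 4.14 |
| 12 | 20 | 20/32 = 63% | 240/32 = 7.50 |
| 6 | 60 | 60/66 = 91% | 360/66 = 5.45 |
| 12 | 60 | 60/72 = 83% | 720/72 = 10.0 |

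A simulation of 400,000 subjects per scenario agrees with the formula. With all at-risk subjects included and those without the event censored, the Kaplan-Meier median at C = 5 was 6.0, 12.02 and 23.85 months for true medians of 6, 12 and 24.

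Over true medians of 3 to 24 months and median observation of 2 to 60 months, the event-only median was always too short:

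- smallest shortfall, M = 3 and C = 60: 180/63 = 2.86, about 5% short
- largest shortfall, M = 24 and C = 2: 48/26 = 1.85, about 92% short

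**Shortest follow-up at the first full analysis.** Two cycles are 2 × 28 = 56 days, and 56/30.4167 = 1.84 months by the SAP's own conversion. Suppose every subject were observed for exactly that long. With rate λ = ln 2/M and F = 1 − exp(−1.84λ), the event-only median is −ln(1 − F/2)/λ. True medians of 3, 6, 12 and 24 months then give 0.82, 0.87, 0.90 and 0.91 months, all close to half the window (0.92). This is the limiting case for the latest enrollees, since subjects enrolled earlier will have been observed for longer if they stayed on study.

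**If some subjects can never have the event.** With half of subjects unable to improve and a true median of 12 months in the rest, the event-only median is 3.5 months at 5-month median observation and 7.5 months at 20-month.

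**The case against.** The strongest reply is that these are openly descriptive tables. Their titles name the subset, N is printed by default, the study has a single arm and no formal hypothesis testing is planned. Section 10.1.2 summarises time to response in responders only, and says so. The primary endpoint, AE incidence, does not depend on these times. All of this stands and limits the consequence. It does not remove the bias. Time to response is accompanied by an overall response rate over all subjects analysed, whereas no Appendix B title announces the share improving among all subjects with baseline neuropathy. Table 14.3.2.16.13.1 gives treatment-emergent neuropathy by baseline status, which partly supplies denominators for worsening. Table 14.3.2.16.13.5, on neuropathy still ongoing at discontinuation, covers only subjects with treatment-emergent neuropathy and neuropathy ongoing at baseline. Baseline neuropathy that simply persisted need not appear there.

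It is also fair that every magnitude above is assumed, and that the titles do not name the median, which comes from the Section 4 default.

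A reader might infer more than the documents support:

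- *That the median measures only observation time.* It does not. M·C/(M + C) is symmetric in the two, and observation dominates only when it is short relative to the event time.
- *That the median cannot exceed typical observation time.* That holds under the exponential assumption. If improvement clustered near 8 months with median observation of 5, the event-only median would be about 8.
- *That subjects who never improve are reported as recovering.* The titles exclude them openly.
- *That Section 8.7 has the same fault.* Its first sentence is restricted: "Dose reductions and interruptions will be summarized for subjects who had at least one dose reduction or interruption". The next sentence, on time to first reduction or interruption and number per subject, states no restriction and includes the frequency of patients. The corresponding Appendix B tables name the Safety Population without a subset.

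**Conclusion.** The point holds for Tables 14.3.2.16.13.3 and 14.3.2.16.13.4 and no further. As written, the plan gives times conditional on the event having been seen, and no other part of the SAP brings in the at-risk subjects without it. The direction of the bias rests on observation ending independently of the neuropathy course. Its size cannot be fixed from the SAP: across the assumed scenarios the shortfall ran from about 5% to about 92%, greatest with short observation and shrinking with longer follow-up. It therefore matters most at the first full analysis. The consequence is confined to the reading of two descriptive tables on an adverse event of special interest, but the correction is cheap and worth making.

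**What to change.** In Section 11.1.1 and Appendix B:

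- **Population.** Improvement or resolution: all safety subjects with neuropathy at baseline. Worsening or new neuropathy: all safety subjects.
- **Censoring.** Censor subjects without the event at the end of their neuropathy/AE observation, or at the data cut-off if earlier, and define that end explicitly. The 28 days after last dose in Section 11.1.1 define treatment emergence. Table 14.3.2.16.16 and Listing 16.2.7.1.2 show that AEs outside that window are also reported.
- **Estimator.** Kaplan-Meier, or cumulative incidence with death as a competing event, with number at risk and number of events.
- **Event-only summary.** It may be kept if labelled as such, with n with the event over n at risk.
- **Time origin.** Use one. Section 11.1.1 counts from enrollment, while the table titles say from baseline, which could mean either the start of the clock or the state against which change is judged.

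The cost is a few lines of SAP wording and two revised table shells; Kaplan-Meier is already planned for the efficacy endpoints. The downside is that some medians may be reported as not reached, particularly at the first full analysis.
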